^c Height will be collected at Day 1 only for subjects \geq 18 years old and at every clinic visit for subjects $<$ 18 years old. Weight should be obtained using a calibrated weight scale and the same scale should be used for a subject throughout the duration of the study. The subject should remove shoes and heavy clothing (sweaters or jackets), and empty pockets. The subject should stand with both feet in the center of the scale with their arms at their side and hold still. Record the weight to the nearest decimal fraction (for example, 25.1 kilograms). For subjects $<$ 18 years of age, measure the weight in triplicate and report the average weight in EDC. A 5% or greater weight loss (whether or not intentional or otherwise explained) should be reported to the medical monitor.

^d The vIGA-AD assessment will be a 5-point scale ranging from clear (0) to severe (4) and is evaluated for the entire body except the scalp, palms, and soles. EASI takes into account overall severity of erythema, infiltration/papulation, excoriation, and lichenification, in addition to extent of BSA affected. The 4 clinical signs will be graded on a 4-point scale (0 [absent] to 3 [severe]) for 4 body regions (head and neck, upper extremities, lower extremities, and trunk). Total EASI score will be calculated as a sum of scores of all 4 body regions. EASI total score will range from 0 (absent) to 72 (severe). Total BSA affected by AD will be determined for all body surfaces except the scalp, palms and soles. vIGA-AD should be completed prior to other physician assessments. SCORAD total score will range between 0 and 103.

Footnotes from table above:

- ^c The WI-NRS pruritus questionnaire will be completed once a week at home utilizing a diary. **The WI-NRS will be self-reported by subjects for subjects ≥ 6 years of age, and reported by parent/guardian for subjects <6 years of age.** During the Phone Visits at Weeks 18, 30, and 44 a reminder will be given to subjects to complete the WI-NRS pruritus questionnaire once a week.
- ^f POEM will be completed by all subjects either by self or by proxy completion (for children unable to read and/or understand the POEM questionnaire, the parent/guardian/caregiver will complete the questionnaire).

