5.4. Final Study Visit – End of Study

The approximate final study visit will occur at Week 52, except for subjects in the Cohort-Week 24, where the final study visit will occur at Week 24. The procedures performed during this visit are as described in the Schedule of Visits and Assessments ([Section 1.3](#)). A 7-day scheduling window is allowed for this visit. Adverse events will be recorded as reported by the participant or and followed to resolution or stabilization (as necessary).

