5.3 Study Day

Study Day will be calculated from the first dose of roflumilast cream 0.15% or 0.05%* in this study, and will be used to show start/end day of assessments or events.

Study Day = (Date of assessment/event – Date of first dose of roflumilast cream in this study) + 1
if date of assessment/event is on or after the date of first dose of roflumilast cream in this study;
= (Date of assessment/event – Date of first dose of roflumilast cream in this study) if date of assessment/event is before the date of first dose of study roflumilast cream in this study.

* Enrollment date (usually the Week 4 visit in the parent study) for enrolled subjects who discontinued early from this study before the first application of roflumilast cream 0.15% or 0.05%.

In the situation where the assessment/event date is partially or completely missing, Study Day will be missing.

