5.4 Windowing Conventions

The scheduled visit will be used to report measurements for summaries by visit regardless of whether this visit was performed within or outside of the analysis visit windows. Unscheduled visit, early termination (ET) visit, and/or retest measurements will only be used for the summaries by visit if a scheduled measurement is not available and the unscheduled/retest/ET measurement

 Innovaderm Research	STATISTICAL ANALYSIS PLAN, Final Version 1.0
Protocol Number: ARQ-151-313	Sponsor: Arcutis Biotherapeutics, Inc.

falls within the analysis visit windows described in [Table 3](#), [Table 4](#), [Table 5](#), and [Table 6](#). Scheduled, unscheduled, ET, and retest measurements will be listed.

If there is more than one assessment for a given analysis visit when a scheduled measurement is not available, the assessment closest to the target day will be considered. If two assessments are equidistant to the target day, the latest assessment will be used.

Table 3 OLE Analysis Visit Windows – vIGA-AD, EASI, BSA Affected by AD, DLQI, CDLQI, IDQOL, DFI, SCORAD, POEM, Vital Signs, Local Tolerability Assessments, PHQ-8, PHQ-A, CDI-2, and C-SSRS

Analysis Visit	Target Day	Window (Days)
OLE Week 4	29	15 to 57
OLE Week 12	85	58 to 127
OLE Week 24	169	128 to 211
OLE Week 36	253	212 to 309
OLE Week 52	365	≥ 310

Table 4 OLE Analysis Visit Windows – WI-NRS

Analysis Visit	Target Day	Window (Days)
OLE Week 1	8	5 to 11
OLE Week 2	15	12 to 18
OLE Week 3	22	19 to 25
OLE Week 4	29	26 to 32
OLE Week x	y	z1 to z2
OLE Week 52	365	≥ 362

where: x= 5 to 51; y= (x * 7) + 1; z1 = y – 3, and z2 = y + 3.

Table 5 OLE Analysis Visit Windows – Clinical Laboratory

Analysis Visit	Target Day	Window (Days)
OLE Week 24	169	15 to 267
OLE Week 52	365	≥ 268

 Innovaderm Research	STATISTICAL ANALYSIS PLAN, Final Version 1.0
Protocol Number: ARQ-151-313	Sponsor: Arcutis Biotherapeutics, Inc.

Table 6 OLE Analysis Visit Windows – Physical Examination

Analysis Visit	Target Day	Window (Days)
OLE Week 4	29	15 to 127
OLE Week 24	169	128 to 267
OLE Week 52	365	≥ 268

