12.2.1 Main Analysis

Missing vIGA-AD secondary efficacy endpoints will be imputed as described in Section 6.2.1. The combined common proportion of subjects achieving each vIGA-AD secondary endpoint will be provided by visit and treatment group (refer to Section 5) along with their combined common two-sided 95% CI. The vIGA-AD success summaries based on the OLE Baseline (refer to Section

 Innovaderm Research	STATISTICAL ANALYSIS PLAN, Final Version 1.0
Protocol Number: ARQ-151-313	Sponsor: Arcutis Biotherapeutics, Inc.

5.2) will only include subjects who have an OLE baseline score other than clear (0) or almost clear (1).

The change and percent change from baseline in WI-NRS score will be summarized among subjects 12 years or older at the start of the parent study* using descriptive statistics by visit and treatment group (refer to Section 5) based on observed cases (i.e., no imputation). Two-sided 95% CI of the mean will also be provided. WI-NRS score will be summarized similarly.

* WI-NRS score, change from baseline and percent change from baseline for subjects < 12 years old at the start of the parent study will be summarized in subgroup analysis (refer to Sections 6.6 and 12.2.3).

The change and percent change from baseline in EASI total score will be summarized using descriptive statistics by visit and treatment group (refer to Section 5) based on observed cases (i.e., no imputation). Two-sided 95% CI of the mean will also be provided. EASI total score will be summarized similarly.

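### The final-week WI-NRS windows in SAP Table 4 are narrower than the permitted exit-visit range, so some compliant completers can have no Week 52 (or Cohort-Week 24 Week 24) itch value

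*SAP*

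**What the plan says.** **Collection.** Footnote to the Schedule in Protocol 1.3: "The WI-NRS pruritus questionnaire will be completed once a week at home utilizing a diary". The WI-NRS row of that schedule is marked at Day 1 only, so no clinic reading is planned at Week 24 or Week 52.

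**Assignment to weeks.** SAP 5.4 Table 4 gives each week a 7-day window around a target day y: "where: x= 5 to 51; y= (x * 7) + 1", with bounds 3 days either side. Week 52 is listed separately, with target Day 365 and an open-ended window from Day 362. SAP 5.3 sets the origin: "Study Day will be calculated from the first dose of roflumilast cream 0.15% or 0.05%* in this study".

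**Exit.** Protocol 5.4 says of the final visit: "A 7-day scheduling window is allowed for this visit". The visit is at Week 52, "except for subjects in the Cohort-Week 24, where the final study visit will occur at Week 24". The Schedule shows the same tolerance of 7 days either side, and marks Study Exit at that visit.

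**Analysis.** Change and percent change in WI-NRS are secondary endpoints, summarised by visit in subjects aged 12 or older on observed cases without imputation (SAP 12.2.1). The 4-point responder endpoint is not imputed either (SAP 12.3.1).

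**Comparison.** SAP Table 3, for the clinic-assessed scales, opens Week 52 at Day 310 and gives Week 24 Days 128-211.

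**The concern.** At the last time point the WI-NRS window begins 3 days before target, but the visit at which the subject leaves may be up to 7 days before target. A subject can follow the protocol exactly, fill in the diary every week, and still have no entry that counts for the final week, because the last one falls in the window of the week before or earlier. Table 3 avoids this for EASI and vIGA-AD, since an early exit visit still lies well inside its windows.

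Two things are at stake. The first is the number of subjects, and so the precision, behind the Week 52 itch summary. The second is the make-up of the Week 24 summary. SAP 3.6 drops analysis by cohort except for specified subgroup endpoints, so 311/312 rollovers from both cohorts are pooled. Cohort-Week 24 adolescents can lose their Week 24 value because they are leaving. Cohort-Week 52 subjects cannot lose theirs for that reason, because their diary continues past Day 172.

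**Working it through.** **Step 1: the plan's own figures.** With target y = 7x + 1 and window y ± 3 (SAP Table 4):
- x = 24: y = 169, window 166-172
- x = 51: y = 358, window 355-361
- x = 52: y = 365, lower bound 362, which agrees with the table.

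**Step 2: exit range.** Target ± 7 (Protocol 1.3 and 5.4) gives Days 358-372 for Week 52 and Days 162-176 for Cohort-Week 24.

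**Step 3: chance of no final-week value by exit day.** Assume one entry every 7 days, an entry due on the exit day counted, a random diary weekday, and assignment by date.

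| Exit day relative to target | Week 52 exit | Cohort-Week 24 exit | Chance of no value |
|---|---|---|---|
| -7 to -4 | 358-361 | 162-165 | 1 |
| -3 | 362 | 166 | 6/7 |
| -2 | 363 | 167 | 5/7 |
| -1 | 364 | 168 | 4/7 |
| 0 | 365 | 169 | 3/7 |
| +1 | 366 | 170 | 2/7 |
| +2 | 367 | 171 | 1/7 |
| +3 to +7 | 368-372 | 172-176 | 0 |

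The first row does not depend on the weekday. The Week 24 window closes at Day 172 while Week 52 stays open, but this does not change the shares: a weekly diary that runs through Day 172 has exactly one entry in a 7-day window.

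**Step 4: share missing overall.** The documents give no distribution of exit days, no diary weekday and no rule on exit-day entries, so each is assumed and varied.

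- Even spread over 15 days: (4 × 1 + (6+5+4+3+2+1)/7)/15 = 7/15 = 46.7%.
- Even spread, last entry always before the exit day: everything moves one day, (5 + 3)/15 = 8/15 = 53.3%.
- Even spread, an entry always made at the exit visit: 4/15 = 26.7%.

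| Exit-day distribution | Exit-day entry counted if due | Last entry before exit day | Entry always made at exit |
|---|---|---|---|
| Even | 46.7% | 53.3% | 26.7% |
| Triangular on target | 43.8-45.1% | 54.9-56.2% | 15.6% |
| Truncated normal, SD 2 to 4 days | 40.0-45.3% | 54.7-60.0% | 3.8-17.0% |
| Skewed late (linear) | 23.3-25.0% | 30.0-31.7% | 8.3% |
| Skewed early (linear) | 68.3-70.0% | 75.0-76.7% | 45.0% |

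In the first two result columns, ranges cover a random weekday and a diary fixed to Days 8, 15, 22 and so on; for the truncated normal they also cover the SD. Results are the same for Week 52 and for Cohort-Week 24.

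If every exit is exactly on target, the loss is 0% with a Day-1-anchored diary filled in that day, and 3/7 = 43% to 4/7 = 57% with a random weekday. These are scenario results, not bounds. In that same anchored case, omitting the exit-day entry leaves Day 358 as the last one, and every subject is missing.

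**Step 5: precision.** Losing a share m widens the 95% CI of a mean by 1/√(1 − m): 1/√0.60 = 1.29 at 40% and 1/√0.533 = 1.37 at 46.7%. This applies at the final week only, and at Week 24 only to the Cohort-Week 24 part of the pooled sample.

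**The case against.** The best counter-argument is in SAP 5.4 itself. A scheduled visit's measurement is reported "regardless of whether this visit was performed within or outside of the analysis visit windows", and the windows serve to place unscheduled, early-termination and retest data. The weekly diary is the planned way of collecting WI-NRS. If each entry carries a nominal week label and counts as scheduled, a Week 52 entry made before Day 362 would be kept and the loss would be smaller. This stands in part: the SAP does not say whether a home entry is a scheduled measurement. But the sentence speaks of visits, there is no WI-NRS visit after Day 1, and Table 4 sets out day ranges for all 52 weeks, which suggests assignment by date.

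Three further objections stand in full.
- The end of diary collection at exit is inferred from Study Exit and the last diary review in the Schedule; no sentence says it.
- A reader might infer that nearly half of completers will lack a final value. The documents do not support that as a finding. It depends on assumed exit timing, and diary review at the exit visit makes an entry on that day plausible, which cuts the loss sharply.
- A reader might also infer that the long-term itch result is lost or biased. The endpoint is defined over time, no document singles out the final week, and no tests are planned. A Week 51 or Week 23 value will usually exist, and the loss follows visit scheduling, with no shown link to itch. Cohort-Week 24 leaves the pooled summary soon after Week 24 in any case.

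**Conclusion.** The mismatch is real and can be read from the documents. Given assignment by date and no entries after exit, completers who exit on Days 358-361 (or 162-165) cannot have a final-week WI-NRS value, and exits on Days 362-367 (or 166-171) carry a 6/7 falling to 1/7 risk with a random weekday.

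The overall share is an assumption: about 40-47% for symmetric exit timing with exit-day entries counted. Across the other scenarios it runs from about 0% (all exits on target, Day-1-anchored diary filled in that day) or 4% (entry always made at a tightly timed exit visit) to 77% (early-skewed exits).

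The consequence is fewer subjects and wider intervals at the last time point of a descriptive secondary endpoint, and a partly artefactual change in who contributes at Week 24 in the pooled 311/312 summary. No bias is shown, and the primary safety endpoints are not touched. This is a cheap improvement worth making.

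**What to change.** Add to SAP 5.4, under Table 4: for Week 52 (Cohort-Week 52 completers) and Week 24 (Cohort-Week 24 completers), only when no entry falls in the Table 4 window, use the last diary entry made on the exit visit day or in the 7 days before it, provided the exit visit is within the protocol's ± 7-day window. State also that diary entries are otherwise assigned by study day.

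For subjects who fill in the diary weekly, this removes the loss, since the 7 days before exit always hold one entry.

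It must be a fallback. Always taking the last entry in the 7 days up to and including exit would replace good in-window Week 24 values for subjects exiting on Days 173-176: (1+2+3+4)/7/15 = about 10% under an even spread. Lowering the Week 52 bound is less tidy. With an even spread, a random weekday and exit-day entries counted, a bound of Day 358 still leaves 20.0% missing and Day 355 leaves 5.7%. Day 352 leaves none, but takes days from Weeks 51 and 50.

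The cost is a sentence or two and minor programming, with no new data. The downside is that the borrowed entry also counts for an earlier week (Week 51 or 50; Week 23 or 22), so it should be flagged in the dataset and footnoted.

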5.5 Derived Variables

All questionnaire scores will be derived by Biostatistics in the ADaM datasets using the formulas defined below, even if calculated scores are present in the EDC database. All pre-calculated scores will be ignored for analysis.

- With the following exception, vIGA-AD Score of Clear (0) or Almost Clear (1) = vIGA-AD of ‘Clear’ (0) or ‘Almost Clear’ (1). The exception is that for subjects who discontinued early from study due to an AE or lack of efficacy, the subject will be considered as not having a vIGA-AD score of Clear (0) or Almost Clear (1) for all pre-specified analysis visits (refer to Section 5.4) for which the subject’s day of last dose falls within or is before the start of the analysis visit window.
- With the following exception, vIGA-AD Success = vIGA-AD of ‘Clear’ (0) or ‘Almost Clear’ (1) plus at least a 2-grade improvement from baseline. The exception is that for subjects who discontinued early from study due to an AE or lack of efficacy, the subject will be considered as not having a vIGA-AD success for all pre-specified analysis visits (refer to Section 5.4) for which the subject’s day of last dose falls within or is before the start of the analysis visit window. vIGA-AD Success will be derived for both the Primary and OLE baselines (refer to Section 5.2)
- Date of last contact = the latest of last study visit date, last dose date, end-of-study date and end-of-treatment date.
- Post-OLE Week 4 study duration (days): The duration can be represented as End Date – Start Date +1. The start date of the Post-OLE Week 4 interval will be the date of the OLE Week 4 visit or OLE Day 29 if the subject missed the OLE Week 4 visit. The end date will be the date of last contact. This endpoint will be calculated only for subjects who enter the post-OLE Week 4 study period.
- Duration (days) of the first BIW dosing will be calculated from the first BIW dosing to the start of the succeeding QD dosing interval. Subject’s last contact date will be used to censor

 Innovaderm Research	STATISTICAL ANALYSIS PLAN, Final Version 1.0
Protocol Number: ARQ-151-313	Sponsor: Arcutis Biotherapeutics, Inc.

this endpoint (time-to-event analysis) or as the end date of this duration (analyzed as a continuous endpoint) for subjects who do not revert to a QD dosing regimen after the first BIW dosing. This endpoint will be calculated only for subjects who enter the post-OLE Week 4 study period with at least one BIW dosing interval.

- Cumulative time (days) on BIW dosing: Subjects may have more than 1 BIW dosing interval. The duration of succeeding BIW dosing intervals will be derived in a manner similar to the first and durations will be summed across all intervals for a subject. This endpoint will be calculated only for subjects who enter the post-OLE Week 4 study period with at least one BIW dosing interval.
- Percent of time on BIW dosing: The cumulative time (days) on BIW dosing will be divided by the Post-OLE Week 4 study duration and multiplied by 100 to measure the percentage of study days on BIW dosing. This endpoint will be calculated only for subjects who enter the post-OLE Week 4 study period with at least one BIW dosing interval.
- Duration (days) of first disease control will be calculated from the first disease control to the time subjects revert to a QD dosing or have a vIGA-AD score ≥ 2 , whichever comes first. Disease control is defined as achievement of a vIGA-AD score of 0, a switch to BIW dosing, and maintenance of a vIGA-AD score of 0 or 1. Disease control starts with the later date of a vIGA-AD score of Clear (0) on or after OLE Week 4 and the switch to BIW dosing. Subject's last contact date will be used to censor this endpoint (time-to-event analysis) or as the end date of this duration (analyzed as a continuous endpoint) for subjects who never lose disease control after the start of the first disease control interval. This endpoint will be calculated only for subjects who enter the post-OLE Week 4 study period and had at least one disease control interval.
- Cumulative time (days) with disease control. Subjects can come in and out of disease control. The duration for each interval will be derived as described above for the first interval. Cumulative time with disease control will sum the durations for all intervals where disease was under control as defined in the previous bullet. This endpoint will be calculated only for subjects who enter the post-OLE Week 4 study period and had at least one disease control interval.
- Percent of time with disease control. The cumulative time with disease control will be divided by the Post-OLE Week 4 study duration and multiplied by 100 to express cumulative time as a percentage of the duration of time that each subject spent in the study after OLE Week 4. This endpoint will be calculated only for subjects who enter the post-OLE Week 4 study period and had at least one disease control interval.

 Innovaderm Research ■■■	STATISTICAL ANALYSIS PLAN, Final Version 1.0
Protocol Number: ARQ-151-313	Sponsor: Arcutis Biotherapeutics, Inc.

- Duration (days) of the first vIGA-AD of Clear (0) will be calculated from the first vIGA-AD score of 0 during the study to the next vIGA-AD score > 0. Subject's last contact date will be used to censor this endpoint (time-to-event analysis) or as the end date of this duration (analyzed as a continuous endpoint) for subjects who never revert to a vIGA-AD score > 0. This endpoint will be calculated only for subjects who had at least one vIGA-AD score of Clear (0) interval.
- Cumulative time (days) with vIGA-AD of Clear (0). Subjects can have more than 1 vIGA-AD of Clear (0) interval. The duration for each interval will be derived as described above for the first interval. Cumulative time with vIGA-AD of 0 will sum the durations for all intervals. This endpoint will be calculated only for subjects who had at least one vIGA-AD score of Clear (0) interval.
- Percent of time with vIGA-AD of Clear (0). The cumulative time will be divided by the study duration and multiplied by 100 to express cumulative time as a percentage of the duration of time that each subject spent in the study. This endpoint will be calculated only for subjects who had at least one vIGA-AD score of Clear (0) interval.
- Duration (days) of the first vIGA-AD of Clear (0) or Almost Clear (1) will be calculated from the first vIGA-AD score of 0 or 1 during the study to the next vIGA-AD score > 1. Subject's last contact date will be used to censor this endpoint (time-to-event analysis) or as the end date of this duration (analyzed as a continuous endpoint) for subjects who never revert to a vIGA-AD score > 1. This endpoint will be calculated only for subjects who had at least one VIGA-AD with a score of Clear (0) or Almost Clear (1) interval.
- Cumulative time (days) with vIGA-AD of Clear (0) or Almost Clear (1). Duration with vIGA-AD score of 0 or 1 measures the duration for the first interval with a VIGA-AD score of 0 or 1. There can be more than 1 interval. Cumulative time with vIGA-AD of 0 or 1 will sum the durations for all intervals. The duration for each interval will be derived as described above for the first interval. This endpoint will be calculated only for subjects who had at least one VIGA-AD with a score of Clear (0) or Almost Clear (1) interval.
- Percent of time with vIGA-AD of Clear (0) or Almost Clear (1). The cumulative time will be divided by the study duration and multiplied by 100 to express cumulative time as a percentage of the duration of time that each subject spent in the study. This endpoint will be calculated only for subjects who had at least one VIGA-AD with a score of Clear (0) or Almost Clear (1) interval.

 Innovaderm Research ■■■	STATISTICAL ANALYSIS PLAN, Final Version 1.0
Protocol Number: ARQ-151-313	Sponsor: Arcutis Biotherapeutics, Inc.

- WI-NRS 4-point Reduction = achievement of a \geq 4-point reduction in weekly? WI-NRS pruritus score from baseline. WI-NRS 4-point reduction will be derived for both the Primary and OLE baselines (refer to Section 5.2)
- EASI Total Score:

Four anatomic sites—head, upper extremities, trunk, and lower extremities—are assessed for erythema, induration/infiltration (papules), excoriation, and lichenification as seen on the day of the examination. The severity of each sign is assessed using a 4-point scale (half steps are allowed e.g., 0.5, 1.5 and 2.5):

- 0 = none
- 1 = mild
- 2 = moderate
- 3 = severe

The area affected by atopic dermatitis within a given anatomic site is estimated as a percentage of the total area of that anatomic site and assigned a numerical value according to the degree of atopic dermatitis involvement as follows:

- 0 = no involvement
- 1 = 1-9%
- 2 = 10-29%
- 3 = 30-49%
- 4 = 50-69%
- 5 = 70-89%
- 6 = 90-100%

The EASI score is obtained by using the formula below for subjects \geq 8 years old:

$$\text{EASI} = 0.1 (E_h + I_h + Ex_h + L_h) A_h + 0.2 (E_u + I_u + Ex_u + L_u) A_u + 0.3 (E_t + I_t + Ex_t + L_t) A_t + 0.4 (E_l + I_l + Ex_l + L_l) A_l$$

The EASI score is obtained by using the formula below for subjects \leq 8 years old:

$$\text{EASI} = 0.2 (E_h + I_h + Ex_h + L_h) A_h + 0.2 (E_u + I_u + Ex_u + L_u) A_u + 0.3 (E_t + I_t + Ex_t + L_t) A_t + 0.3 (E_l + I_l + Ex_l + L_l) A_l$$

 Innovaderm Research ■■■	STATISTICAL ANALYSIS PLAN, Final Version 1.0
Protocol Number: ARQ-151-313	Sponsor: Arcutis Biotherapeutics, Inc.

Where E, I, Ex, L, and A denote erythema, induration, excoriation, lichenification and area, respectively, and h, u, t, and l denote head, upper extremities, trunk, and lower extremities, respectively.

Note: Palms and soles may be treated with investigational product in this study, but will not be counted towards IGA, EASI, or BSA assessments. EASI is evaluated for the entire body except the scalp, palms, and soles.

Note: If a subject turns 8 years old during the study, the formula used at Screening of the preceding study will continue to be used through the duration of the subject's participation in this study.

- EASI-50, EASI-75, EASI-90, EASI-100 - Achievement of at least a 50%, 75%, 90%, or 100% reduction from baseline in the EASI total score.
- DLQI Total Score = sum of the 10 questions (individual questions scored as Very much=3, A lot=2, A little=1, Not at all=0, Not relevant=0, Question 7: Yes=3, if No, then follow the same score as A lot, A little, Not at all), ranging from 0 to 30. If 1 item is missing, it is scored as 0 for that item. If 2 or more items are missing, the score should not be calculated. The DLQI will be performed for the subject with age 17+ years based on age at start of preceding studies ARQ-151-311/312/315.
- CDLQI Total Score = sum of the 10 questions (individual questions scored as Very much=3, Quite a lot=2, Only a little=1, Not at all=0; Question 7: if the last week was school time, the question was scored as Very much=3, Quite a lot=2, Only a little=1, Not at all=0, with Prevented school recoded to 3, and if the last week was holiday time, the standard responses apply), ranging from 0 to 30. If 1 item is missing, that item is scored as 0. If 2 or more items are missing, the score should not be calculated. The CDLQI will be performed for the subjects with age >4 and <16 years based on age at start of preceding studies ARQ-151-311/312/315.
- IDQOL Total Score = sum of the 10 questions (individual question 1 scored as All the time= 3, A lot= 2, A little= 1, None= 0; individual question 2 scored as: Always crying, extremely difficult= 3, Very fretful= 2, Slightly fretful= 1, Happy= 0; individual question 3 scored as More than 2 hours= 3, 1 – 2 hours= 2, 15 minutes – 1 hour= 1, 0 – 15 minutes= 0; individual question 4 scored as 5 hours or more= 3, 3 – 4 hours= 2, 1 – 2 hours= 1, Less than 1 hour= 0; individual questions 5 to 10 scores as Very much= 3, A lot= 2, A little= 1, Not at all/None= 0), ranging from 0 to 30. If 1 item is missing, that item is scored as 0. If 2 or more items are missing, the score should not be calculated. Of note, the severity of eczema question is scored and reported separately than the IDQOL total score. The IDQOL

 Innovaderm Research ■■■	STATISTICAL ANALYSIS PLAN, Final Version 1.0
Protocol Number: ARQ-151-313	Sponsor: Arcutis Biotherapeutics, Inc.

will be completed by parents/caregivers for subjects with age < 4 years based on age at start of the preceding study ARQ-151-315.

- DFI Total Score = sum of the 10 questions (individual questions scored as Very much=3, A lot=2, A little=1; Not at all=0) ranging from 0 to 30. If 1 item is missing, it is scored as 0 for that item. If 2 or more items are missing, the score should not be calculated. The DFI will be completed by parents/caregivers for all subjects \geq 2 years of age and \leq 17 years of age. Please note that the DFI is not to be conducted for subjects who were \leq 17 years of age in the ARQ-151-311/312 studies and turned 18 years of age prior to enrollment into ARQ-151-313.
- PHQ-8 Total Score = sum of the 8 questions (individual questions scored as Not at all=0, Several days=1, More than half the days=2, and Nearly every day=3), ranging from 0 to 24. If more than 1 item is missing the score should not be calculated. If 1 item is missing the score is calculated as (sum of answered items*8)/number of answered items (i.e., 7). The PHQ-8 Assessment will be performed in adult subjects based on age at start of preceding studies ARQ-151-311/312.
- Modified PHQ-A Total Score = sum of the 8 questions (individual questions scored as Not at all=0, Several days=1, More than half the days=2, and Nearly every day=3), ranging from 0 to 24. If more than 1 items is missing the score should not be calculated. If 1 item is missing, the score is calculated as (sum of answered items*8)/number of answered items (i.e., 7). The Modified PHQ-A Assessment will be performed in adolescent subjects (12-17 years old, inclusive) based on age at start of preceding studies ARQ-151-311/312.
- CDI-2 Total Score = sum of the 17 questions (individual questions Q2, Q7, Q13, Q14, and Q16 scored as Much or most of the time=0, Often=1, Some of the time=2, Not at all=3; individual questions Q1, Q3 to Q6, Q8 to Q12, Q15, and Q17 scored as Much or most of the time=3, Often=2, Some of the time=1, Not at all=0), ranging from 0 to 51. If more than 2 items are missing the total score should not be calculated. If 1 item is missing the total score is calculated as (sum of answered items*17)/number of answered items (i.e., 16). If 2 items are missing the total score is calculated as (sum of answered items*17)/number of answered items (i.e., 15). The CDI-2 Assessment will be performed for subjects 6 to 11 years old, inclusive based on age at start of preceding studies ARQ-151-311/312/315.
- CDI-2 Emotional Problem Subscale Score = sum of 9 questions (Q1, Q3-6, Q8, Q10-12). If more than 1 item is missing the subscale score should not be calculated. If 1 item is missing the subscale score is calculated as (sum of answered items*9)/number of answered items (i.e., 8).

 Innovaderm Research ■■■	STATISTICAL ANALYSIS PLAN, Final Version 1.0
Protocol Number: ARQ-151-313	Sponsor: Arcutis Biotherapeutics, Inc.

- CDI-2 Functional Problem Subscale Score = sum of 8 questions (Q2, Q7, Q9, Q13-17). If more than 1 item is missing the subscale score should not be calculated. If 1 item is missing the subscale score is calculated as (sum of answered items*8)/number of answered items (i.e., 7).
- POEM Total Score = sum of the 7 questions (individual questions scored as No days = 0, 1 to 2 days = 1, 3 to 4 days = 2, 5 to 6 days = 3, Every day = 4), ranging from 0 to 28. If 1 question is left unanswered, this question is scored 0 and the total score is calculated as usual out of a maximum of 28. If 2 or more questions are left unanswered, the questionnaire total score should not be calculated.
- SCORAD Total Score = [Overall BSA affected by AD / 5] + [Intensity score * 7/ 2] + Subjective symptoms score (i.e., pruritus + sleep loss), ranging from 0 to 103. SCORAD total score will be set to missing if information for any of the three measures is missing.
- Change from baseline = Assessment value at post-baseline visit X – baseline value.
- Percent change from baseline = (Assessment value at post-baseline visit X – baseline value) × 100% / (baseline value)

Percent change from baseline will be missing in situation where baseline value equals to 0.

- Exposure-adjusted incidence rate (EAIR) = (number of subjects with an event / total within-arm exposure [days]) * 365.25 days/year * 100.
- BMI (kg/m²) = (weight in kg)/ [(height in cm/100)²]. For child and adolescent (2 to 17 years), after BMI is calculated, it is expressed as a percentile using data files and instructions provided by the CDC (https://www.cdc.gov/growthcharts/percentile_data_files.htm).

